model has suggested that NPC sparing radiation may allow improved survival of neural progenitor cells compared to conventional radiation treatment plans, at least at an early time point (34).

Given the potential benefit of NPC in reducing the neurocognitive toxicity of radiation, but the unclear relationship between radiation dose to the NPC containing niches and tumor control, the purpose of this trial is to examine local recurrence at 1 year using a modified radiation technique which attempts to spare the NPC containing niches of the brain as much as possible without compromising tumor coverage during adjuvant radiation therapy plus temozolomide for GBM. If this study demonstrates that NPCsparing radiation does not adversely influence local recurrence in the spared region of the brain, we plan to design a randomized controlled trial to evaluate neurocognitive outcomes in brain tumor patients treated NPC-sparing RT versus conventional RT.

2.2 **Temozolomide**

Temozolomide is an oral alkylating agent that interferes with DNA replication in a schedule-dependent manner. The therapeutic benefit of the drug depends on its ability to alkylate or methylate DNA at the N-7 or O-6 position of guanine residues, which results in DNA damage and cell death. Some tumor cells produce an enzyme called O-6-methylguaninine methyltransferase (MGMT) which repairs the DNA damage and decreases the therapeutic benefit of temozolomide (35). Epigenetic silencing of MGMT by some tumor cells prevents synthesis of the enzyme resulting in tumors that are more sensitive to killing by temozolomide. Similarly, MGMT presence in GBM cells predicts for poor response to the drug. Toxicities associated with temozolomide include nausea, vomiting, infertility, teratogenicity, alopecia, fatigue, headache, constipation, anorexia, convulsions, rash, hemiparesis, diarrhea, asthenias, fever, dizziness, coordination abnormal, viral infection, amnesia, insomnia, lymphopenia, thrombocytopenia, neutropenia, and leucopenia, allergic reactions.

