8.4 Statistical Methods of Analysis

All analysis will be based on the Intend-To-Treat (ITT) principle. Per-protocol will be allowed after ITT analyses.

The proportion of patients with LR in the avoidance region of the NPC will be estimated along with the exact 95% confidence interval. The lower bound 95% confidence interval of exact binomial distribution will be used to determine the acceptance of the LR rate of 25%.

All patients will count towards assessment of all objectives. However, if no patient relapses in the spared NPC containing region, we recognize that the present study will not definitively demonstrate that sparing of the NPC regions does not impact the pattern of recurrence since this is a pilot study and 2 patients received mebendazole following completion of radiation therapy but prior to relapse. Given that no intervention to date including systemic agents, radiation dose escalation, and hypofractionation has ever impacted the site of recurrence we feel it is exceedingly unlikely that mebendazole would impact our primary endpoint. However, we will evaluate if the analysis of the primary endpoint would yield different results with or without inclusion of these patients. If there is a difference both analyses will be presented in the manuscript. Even if there is no statistically significant difference

between the groups we will clearly state in our publications that 2 patients received mebendazole with their adjuvant temozolomide following completion of radiation therapy but prior to relapse.

To quantify the extent of radiation dose sparing to the NPC containing regions that is possible, patients will be binned into 4 groups according to the volume of NPC region that receives a certain dose as follows: 1) $V_{5Gy} \le 50\%$; 2) $V_{5Gy} \le 20\%$; 3) $V_{10Gy} \le 20\%$; 4) Doses higher than levels 1-3. The proportion of overall patients who meet at least the dose constraint will be estimated using a binomial distribution along with 95% confidence intervals, as well as the individual group.

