8.5 Interim Disease Progression Monitoring

Based on the unpublished data from the New approaches to Brain Tumor Therapy Consortium, the median time of progression was 8.5 months among the newly diagnosed GBM treated by RT+TMZ (standard). The progression area outside radiation bed was about 20%. This study does not anticipate an above 30% progression rate in the spared NPC containing region. We expect a less than 30%, about 20% progression rate in the spared NPC containing region. However, we plan to monitory the progression rate throughout the trial. The progression rate in the spared NPC containing region will be monitored continuously throughout the cohort using the Bayesian stopping rule at patient numbers 10 and 20, after patients have a minimum of 6 months follow-up. We consider a 30% progression rate the highest limit that permits to continue this study and will stop early if there are excesses. The number of patients experiencing progression in the spared NPC containing region was assumed to follow a binomial distribution. Given the planned sample size of 30, a stopping boundary would be reached if the proportion of patients experiencing progression in the spared NPC containing region exceeds 30% with a posterior probability ≥ 0.6 . A recommendation for early stopping if 4 or more out of 10, or 7 or more out of 20 patients had disease progression in the spared NPC containing region. The probability of meeting the stopping boundary is 0.56 under a true probability of progression is 0.3.

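### At the interim stopping boundary, sections 8.5 and 8.4 give opposite answers about recurrence in the spared region, and the plan does not say which one decides

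*Combined protocol and SAP*

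**What the plan says.** **Section 8.5 (interim monitoring).** Progression in the spared region is reviewed "using the Bayesian stopping rule at patient numbers 10 and 20, after patients have a minimum of 6 months follow-up". The limit is 30%: "We consider a 30% progression rate the highest limit that permits to continue this study". The boundary is reached when the rate "exceeds 30% with a posterior probability ≥ 0.6", which is turned into counts: "A recommendation for early stopping if 4 or more out of 10, or 7 or more out of 20 patients had disease progression". One operating characteristic is given: "The probability of meeting the stopping boundary is 0.56 under a true probability of progression is 0.3".

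**Section 8.4 (final analysis).** All patients count, under intention to treat, and "The lower bound 95% confidence interval of exact binomial distribution will be used to determine the acceptance of the LR rate of 25" (per cent). The section does not mention the interim looks.

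**Section 2.1 (use of the result).** If the study shows that NPC-sparing "radiation does not adversely influence local recurrence in the spared region of the brain, we plan to design a randomized controlled trial".

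Neither 8.4 nor 8.5 refers to the other. No section says what conclusion or analysis follows a stop.

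**The concern.** Section 8.5 stops the trial because progression in the spared region looks higher than 30%. Section 8.4 accepts a lower rate, 25%, whenever the data cannot exclude it from below. With 10 or 20 patients the lower limit is far below the observed proportion, so counts high enough to stop the trial can still pass the final rule. One trial could then be reported as stopped for excess progression and also as having met its primary criterion. That criterion is the plan's only formal test of whether the recurrence rate is acceptable, and the planned randomized trial depends on a favourable answer.

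**Working it through.** **Inputs.** Sample size 30, looks at 10 and 20 patients, boundaries of at least 4/10 and 7/20, and a binomial model (8.5). Acceptance threshold 25% on the exact lower 95% limit (8.4). I read acceptance as a lower limit at or below 25%, with a two-sided 95% interval.

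**Step 1: the plan's own figure.** At a true rate of 0.30:

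- P(X10 ≥ 4) = 0.350
- P(X10 ≤ 3 and X20 ≥ 7) = 0.135
- The two printed looks together: 0.350 + 0.135 = 0.485, not the stated 0.56
- Adding a boundary of 10 or more of 30: P(no earlier crossing and X30 ≥ 10) = 0.076, total 0.561

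So 0.56 is reproduced only with a third boundary that 8.5 does not print. Section 8.5 states no prior. Under Beta(1,1), Beta(0.6,1.4) and Beta(3,7) priors alike, 4/10, 7/20 and 10/30 are the smallest counts with posterior probability at least 0.6.

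**Step 2: the 8.4 limit at the 8.5 counts.** The exact lower limit is the 0.025 quantile of Beta(x, n − x + 1).

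| Count | Lower limit | 8.5 | 8.4 |
|---|---|---|---|
| 4/10 | 12.2% | stop | accept |
| 5/10 | 18.7% | stop | accept |
| 6/10 | 26.2% | stop | do not accept |
| 7/20 | 15.4% | stop | accept |
| 8/20 | 19.1% | stop | accept |
| 9/20 | 23.1% | stop | accept |
| 10/20 | 27.2% | stop | do not accept |

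At n = 30 the last accepted count is 12 (22.7%); 13/30 gives 25.5%. The unprinted boundary clashes too: 10 to 12 of 30 would meet it and be accepted.

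**Step 3: how often a crossing trial is accepted, with one common rate.**

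- Analysed at the look, true 30%: P(X10 = 4 or 5) + P(X10 ≤ 3, X20 = 7 to 9) = 0.303 + 0.131 = 0.434; 0.434/0.485 = 90%.
- Analysed at the look, true 40%: 0.622/0.802 = 78%.
- All 30 analysed: P(crossed and X30 ≤ 12) / P(crossed) = 0.402/0.485 = 83% at a true 30%, and 0.386/0.802 = 48% at 40%.

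**Step 4: the whole design.** Acceptance with all 30 analysed equals that of a single analysis at n = 30. The last column treats every crossing as a stop and as not meeting the criterion.

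| True rate | P(cross) | Accept, analysed at look | Accept, all 30 analysed | Accept, stop = not met |
|---|---|---|---|---|
| 20% | 0.157 | 0.993 | 0.997 | 0.843 |
| 25% | 0.306 | 0.979 | 0.978 | 0.693 |
| 30% | 0.485 | 0.948 | 0.916 | 0.513 |
| 35% | 0.660 | 0.894 | 0.780 | 0.337 |
| 40% | 0.802 | 0.815 | 0.578 | 0.193 |
| 50% | 0.956 | 0.595 | 0.181 | 0.039 |

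**Step 5: sensitivity.**

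- *One-sided 95% limit:* 87% (true 30%) and 74% (true 40%) of crossing trials are accepted at the look.
- *Number enrolled at the first look:* at 3 to 4 per month (8.2.2), 10 + 6 × 3 = 28, or 10 + 6 × 4 = 34, capped at 30, are enrolled when the tenth patient is 6 months from entry. At the Schema's 4 to 5 per month, all 30 are. If accrual takes 1 to 2 years (also 8.2.2), about 25 down to 17 are. With 17 to 28 analysed, overall acceptance at a true 40% is 0.75 down to 0.66, against 0.58 for all 30.
- *Events after the look (assumption: 50% to 80% of 1-year events have occurred by then, look patients only analysed):* 62% to 80% of stopped trials are accepted at a true 30%, and 40% to 63% at 40%. Overall acceptance is 0.912 to 0.925 against 0.916 at 30%, and 0.60 to 0.71 against 0.58 at 40%.

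**The case against.** **The plan never says that a stopped trial goes through 8.4.** This is fair. A reader might infer that the sponsor would declare a stopped trial acceptable; the documents do not say so. Section 8.2.1 ties the estimate to 30 patients, and 8.4 concedes that even zero relapses in the region would not be definitive. But 8.4 states its criterion without exception and 8.5 calls the stop a recommendation, so nothing prevents the contradictory reading.

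**The interim looks need not increase false acceptance.** A reader might infer from 0.82 against 0.58 at a true 40% that early stopping always does this. The documents do not support that. The rise needs fewer than 30 patients in the analysis and is large only with far fewer. No accrual pause is stated, and at the stated monthly rates most or all patients are enrolled by the first look. With all 30 analysed there is no rise. Nor do the looks inflate the chance of wrongly finding a rate above 25% (0.021 with them, 0.022 without, at a true 25%).

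**The interim and final data differ.** This also stands. The looks use at least 6 months of follow-up and the endpoint (8.1.2) is at 1 year. Later events lower the shares, as in Step 5, but do not remove the conflict.

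**The lower-limit rule is the real fault.** Largely true. A single analysis of 30 already accepts 92% of the time at a true 30% and 58% at 40%. Under an upper-limit criterion, acceptance would need at most 1/20 or 2/30 and would be impossible at 10, so no trial analysed at its stopping look could pass. Even then, the plan would not say what a stop means for the conclusion.

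**A sensitive safety trigger need not settle the final estimate.** True in principle: the boundary is crossed in 15.7% of trials at a true 20%. That is a reason to state the consequence of a stop and its cost.

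**Conclusion.** Wrong as written. At 4 or 5 of 10 and 7 to 9 of 20, section 8.5 recommends stopping for a rate above 30% while 8.4 accepts 25%. This follows from the exact limits alone and rests only on reading acceptance as a lower limit at or below 25%. How often it happens also rests on a common binomial rate: 90% and 78% of crossing trials (true 30% and 40%) if analysed at the look, 83% and 48% if all 30 are analysed, and less if 1-year events accrue after the look. The size comes mainly from the lower-limit criterion. Higher overall false acceptance is conditional on a reduced analysis set and should not be presented as a general property of the design.

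**What to change.** 1. State in both 8.4 and 8.5 that a trial stopped under 8.5 is not declared to have met the 25% LR criterion. Its LR rate is reported with an exact interval on all treated patients, as an estimate only.
2. Correct the lower-limit criterion in 8.4 in the same revision, since it causes most of the conflict.
3. Replace the single figure in 8.5 with the probabilities of stopping and of acceptance under the combined rule at true rates of 20%, 25%, 30% and 40%.
4. Reconcile 0.56 with the two printed looks, which give 0.485: either print the third boundary or correct the figure.

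This takes a few sentences and a short exact calculation, with no extra patients or data. The price should be disclosed. If every crossing leads to a stop and the lower-limit criterion is otherwise unchanged, acceptance falls from 0.99 to 0.84 at a true 20% and from 0.98 to 0.69 at 25%. In return it falls from 0.82 (0.58 if all 30 are analysed) to 0.19 at 40%. A trial stopped at 4/10 whose enrolled patients end at 4/30 (13%, interval 3.8% to 30.7%) would not be declared to have met the criterion; reporting the estimate keeps that information available.

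### The two listed early-stopping looks (≥4/10 or ≥7/20) cross with probability 0.485 at a true rate of 30%, not the stated 0.56

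*Combined protocol and SAP*

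**What the plan says.** Section 8.5 (Interim Disease Progression Monitoring) says that progression in the spared region "will be monitored continuously throughout the cohort using the Bayesian stopping rule at patient numbers 10 and 20", once patients have at least 6 months of follow-up. The number of patients with such progression "was assumed to follow a binomial distribution". The boundary is defined by a posterior probability of at least 0.6 that the rate exceeds 30%; the prior is not given. The rule is then turned into counts of patients who progress within the spared niche: "A recommendation for early stopping if 4 or more out of 10, or 7 or more out of 20 patients had disease progression". The section closes with its one operating characteristic: "The probability of meeting the stopping boundary is 0.56 under a true probability of progression is 0.3".

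The planned sample size of 30 is mentioned when the boundary is introduced, but no count is listed at 30. On the expected rate the section says: "We expect a less than 30%, about 20% progression rate in the spared NPC containing region".

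**The concern.** The section gives everything needed to compute the crossing probability: two look times, two counts, a binomial model and a true rate. The result should match the stated 0.56, and it does not.

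This rule is the trial's guard against excess progression in tissue that is deliberately spared, and the plan treats 30% as the highest rate at which the study may continue. Someone reading 0.56 as the property of the listed looks would believe that a trial sitting at that limit is more likely than not to be flagged. With the listed counts it is slightly more likely to pass both looks than to be flagged. The section also gives no figure at the rate it expects, so the chance of a false alarm cannot be read from the plan.

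**Working it through.** **Inputs, all from section 8.5.** Looks at n = 10 and n = 20; boundaries ≥4 and ≥7; independent binomial outcomes; true rate p = 0.3; stated result 0.56.

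**Formula.** Let X10 and X20 be the cumulative numbers of progressions. The probability of crossing is

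P(X10 ≥ 4) + P(X10 ≤ 3 and X20 ≥ 7).

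The second term sums, over k = 0 to 3, P(X10 = k) × P(at least 7 − k events in the next 10 patients).

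**First look.** P(X10 ≥ 4) = 0.3504.

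**Second look, among trials that passed the first.**

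| Events in first 10 (k) | P(X10 = k) | Needed in next 10 | Probability | Product |
|---|---|---|---|---|
| 0 | 0.0282 | ≥7 | 0.0106 | 0.0003 |
| 1 | 0.1211 | ≥6 | 0.0473 | 0.0057 |
| 2 | 0.2335 | ≥5 | 0.1503 | 0.0351 |
| 3 | 0.2668 | ≥4 | 0.3504 | 0.0935 |
| Sum | | | | 0.1346 |

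**Total for the listed rule.** 0.3504 + 0.1346 = 0.4850, so 1 − 0.4850 = 0.5150 of trials pass both looks. A simulation of 2,000,000 trials gave 0.4848. The gap from the stated figure is 0.56 − 0.485 = 0.075. The two listed looks reach 0.56 only at a true rate of 32.1%.

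**Attempts to reproduce 0.56 at p = 0.3.**

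- Adding the two marginal tail probabilities: 0.3504 + 0.3920 = 0.742.
- Treating the two looks as independent: 1 − (1 − 0.3504)(1 − 0.3920) = 0.605.
- Neighbouring counts: ≥4/10 or ≥8/20 gives 0.403; ≥4/10 or ≥6/20 gives 0.616; ≥3/10 or ≥7/20 gives 0.658.
- Adding a third check at 30: ≥10/30 adds 0.0756, for a total of 0.5606. With ≥9/30 the total is 0.642, and with ≥11/30 it is 0.513.
- Applying the posterior rule after every patient from 10 to 20: 0.557 under several priors that also yield 4/10 and 7/20, such as Beta(0.6, 1.4) and Beta(3, 7). Other priors yielding the same two counts give different answers: Beta(6, 14) 0.525, Beta(2, 5) 0.539, Beta(1, 2) 0.573, Beta(0.5, 0.5) 0.607, Beta(1, 1) 0.627.

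All the priors named in the last item also put the boundary at 10/30 when the rule is applied at 30 patients. The listed counts therefore do not identify the prior.

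**Other true rates.**

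| True rate | Two listed looks | With ≥10/30 added |
|---|---|---|
| 0.20 | 0.157 | 0.172 |
| 0.25 | 0.306 | 0.350 |
| 0.30 | 0.485 | 0.561 |
| 0.40 | 0.802 | 0.884 |

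**The case against.** The strongest reply is that 0.56 is a correct figure for a rule that was only partly written down. The section defines its boundary by the posterior criterion and mentions the sample size of 30 in the same sentence. The counts at 10 and 20 come separately, as recommendations for early stopping, and the 0.56 sentence refers to the boundary. Under many plausible priors the criterion applied at 10, 20 and 30 patients gives 4, 7 and 10, and the crossing probability is 0.5606. On that reading nothing was miscalculated, 44% is the chance of never crossing at any of the three points, and replacing 0.56 with 0.485 would remove a valid number. The text also speaks of continuous monitoring, and checking after each patient from 10 to 20 can give 0.557. Finally, those monitoring the trial act on the counts, not on 0.56, and neither the sample size nor the primary analysis uses it.

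Much of this stands as an account of where 0.56 may have come from, and the three-point version is a close match. It does not make the text right. No boundary at 30 is listed, and a crossing at 30 comes at full enrolment, so it cannot be an early stop. The sentence that mentions continuous monitoring ties the rule to patients 10 and 20, and the continuous reading gives anything from 0.525 to 0.627 depending on a prior the plan does not state. Two different unlisted schemes both land near 0.56, so the origin of the figure cannot be settled from the document. It is also true that the counts, the sample size and the primary analysis are unaffected, which limits the consequence.

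**Conclusion.** The point holds. For the two looks and counts listed in section 8.5, the probability of crossing at a true rate of 30% is 0.485. The stated 0.56 is 7.5 percentage points higher and does not describe the rule as written. The result is exact, rests only on the binomial model and the printed counts, and needs no assumption about the prior. Calling 0.56 an overstatement applies to the listed looks. If a check at 30 was intended, the defect is an incomplete rule instead of a wrong probability. In either case the rule and its only operating characteristic do not match. This should be fixed, but it does not invalidate the boundary counts.

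**What to change.** First state in section 8.5 the prior actually used and whether any look beyond patients 10 and 20 is intended. Then choose the matching wording:

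- If only the two listed looks apply, replace 0.56 with 0.485 as the early-stopping probability at a true rate of 30%, and add 0.157 at 20% and 0.802 at 40%.
- If a check at 30 patients was intended, list ≥10/30, label it a final check and not an early stop, and keep 0.56 as the overall crossing probability, with 0.172 at 20% and 0.884 at 40%.
- If other looks are intended, list their counts and report the probability that goes with them.

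For the first two options the cost is one or two sentences. The counts at 10 and 20, the sample size and the conduct of the trial stay as they are. The first option lowers the reported probability at 30%; the second adds one final check to the listed rule.

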9. ADVERSE EVENTS AND RECORDING

9.1 **Definition of Adverse Event (AE)**

An adverse event is the development of an undesirable medical condition or the deterioration of a pre-existing medical condition during or following an exposure to a treatment, whether or not considered causally related to the treatment. An undesirable medical condition may be symptoms (headache, nausea), signs (tachycardia, enlarged liver), or abnormal results of an investigation (MRI, laboratory finding). In clinical trials, from the time of signing an informed consent, an AE may include an undesirable medical condition, occurring at any time, even if no trial treatment has been administered.

9.2 Radiation Related Adverse Events

Risks Associated with Brain Radiation Therapy:

Very Likely

- Scalp redness or soreness
- Hair loss
- Dry mouth or altered taste
- Fatigue, sleepiness
- Skin redness or soreness in the ear canal

Less Likely, But Serious

- Permanent hair loss
- Hearing loss
- Eye injury resulting in vision loss or even blindness
- Mental slowness, behavioral changes
- Severe damage to normal brain tissue that may require additional surgery
- Brain damage, which could affect judgment, memory, sensation, or ability to control movement

Less Likely

- Fever, chills, heavy sweating
- Upset stomach, nausea and/or vomiting
- Loss of appetite
- Headaches, seizure, weakness

All radiation related adverse events will be recorded on the local toxicity case report forms.

9.3 Chemotherapy Related Adverse Events

Risks associated with Temozolomide:

Very Likely

- Nausea and/or vomiting
- Headache
- Constipation
- Drowsiness/Fatigue
- Insomnia (trouble sleeping)
- Skin rash
- Swelling

Less Likely, But Serious

- Decrease in blood counts that may cause infection and bleeding
- Decreased ability to carry out daily activities
- Pneumonia
- Increased blood sugar
- Pain when swallowing
- Internal bleeding
- Seizure
- Subsequent development of leukemia

Less Likely

- Loss of appetite
- Diarrhea
- Fever
- Weight loss
- Weakness
- Sores in your mouth
- Hair loss
- Weakness of hands and feet
- A temporary elevation in the blood tests that show how your liver is functioning
- Shortness of breath
- Confusion
- Blurred vision
- Allergic reactions
- Chills
- Body aches
- Coughing

The adverse events (both hematologic and non-hematologic) that patients experience due to chemotherapy will be recorded on appropriate case report forms only if they are greater than or equal to grade 3, result in a delay in treatment, or are required to be reported per institutional guidelines.

